7.1.2 Key Secondary Efficacy Endpoints

The key secondary efficacy endpoints include the following, with each dose (Phase 2) or the optimal dose (Phase 3) of FP-025 compared to placebo:

- Proportion of patients on invasive mechanical ventilation at Day 28;
- Proportion of patients alive at Day 28;
- Proportion of patients alive and not requiring non-invasive or invasive ventilation (ie, not receiving high-flow nasal cannula, non-invasive positive pressure ventilation, invasive mechanical ventilation, or ECMO) at Day 60;
- Proportion of patients on invasive mechanical ventilation at Day 60; and
- Proportion of patients alive at Day 60.

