7.1.3 Other Secondary Efficacy Endpoints

The other secondary efficacy endpoints include the following, with each dose (Phase 2) or the optimal dose (Phase 3) of FP-025 compared to placebo:

- Quantitative assessment of lung fibrosis at Day 28 and at Day 60 using high-resolution, non-contrast CT scan;
- Proportion of patients who were randomized on invasive mechanical ventilation who are free of invasive mechanical ventilation at Day 28 and at Day 60;
- Number of ventilator-free days (ie, days free of invasive mechanical ventilation) at Day 28 and at Day 60;
- Number of ICU-free days at Day 28 and at Day 60;
- Number of days in the hospital at Day 28 and at Day 60;
- Change from baseline in peripheral capillary oxygen saturation (SpO₂) at Day 28 and at Day 60;
- Change from baseline in PaO₂/FiO₂ ratio at Day 28 and at Day 60 (patients on invasive or non-invasive ventilation only);
- Proportion of patients alive and not hospitalized at Day 28 and at Day 60;

- Proportion of patients with disease progression (defined as a ≥ 2 -point decrease in the NIAID 8-point ordinal scale score or death) at Day 28 and at Day 60;
- Proportion of patients who improve by ≥ 2 points on the NIAID 8-point ordinal scale scores at Day 28 and proportion of patients who improve by ≥ 2 points at Day 60;
- Pulmonary function at Day 28 (if possible based on the patient's clinical condition per the judgment of the Investigator) and at Day 60 (all patients) based on the following scores:
 - Forced vital capacity (FVC);
 - Forced expiratory volume in 1 second (FEV₁);
 - FEV₁/FVC ratios; and
 - Diffusing capacity of the lungs for carbon monoxide; and
- Change from baseline in eGFR, blood urea nitrogen, and serum creatinine at Day 28 and Day 60.

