9 STATISTICS

9.1 Analysis Populations

The following analysis populations are defined for this study:

Intent-to-Treat (ITT) Population: The ITT Population is defined as all randomized patients. The ITT Population will be the primary population for analysis of efficacy data. Efficacy analyses will be based on the assigned treatment group.

Safety Population: The Safety Population is defined as all randomized patients who receive at least 1 dose of study drug. All safety data will be analyzed using the Safety Population. Safety analyses will be based on the treatment actually received.

Per-Protocol (PP) Population: The PP Population is defined as all patients in the ITT Population who complete the study with no major protocol deviations that may impact the primary efficacy assessment. The primary analysis will be repeated on the PP Population. Major protocol deviations will include violations of key entry criteria or deviations that could significantly impact the assessment or interpretation of efficacy data.

PK Population: The PK Population is defined as all patients with at least 1 PK measurement drawn during the study.

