9.2.1.2 Secondary efficacy analysis

The key secondary endpoints of the proportion of patients alive and not requiring non-invasive or invasive ventilation (ie, not receiving high-flow nasal cannula, non-invasive positive pressure

ventilation, invasive mechanical ventilation, or ECMO) at Day 60, the proportion of patients on invasive mechanical ventilation at Day 28 and at Day 60, and the proportion of patients alive at Day 28 and Day 60, will be analyzed using the same method as for the primary analysis.

Tipping point method will be used as a sensitivity analysis for evaluating the robustness of the results for the primary endpoint and key secondary endpoints.

Other secondary endpoints will be analyzed as described in the SAP. For all endpoints defined by events, the time points are defined as the number of days after randomization.

The Phase 2 study is not powered. No alpha controlling strategy will be implemented.

9.2.1.3 Multiplicity in Phase 3

To control the overall Type I error in the final analysis for Phase 3, a fixed sequential testing procedure will be implemented. In a hierarchical step-down manner, the primary efficacy endpoint will be tested at the 1-sided 0.025 level first, followed by testing the secondary efficacy endpoints at the 1-sided 0.025 level in the following hierarchical manner: (1) proportion of patients on invasive mechanical ventilation at Day 28, (2) proportion of patients alive at Day 28, (3) proportion of patients alive and not requiring non-invasive or invasive ventilation (ie, not receiving high-flow nasal cannula, non-invasive positive pressure ventilation, invasive mechanical ventilation, or ECMO) at Day 60, (4) proportion of patients on invasive mechanical ventilation at Day 60, and (5) proportion of patients alive at Day 60.

Inferential conclusions about these efficacy endpoints will require statistical significance of the previous endpoints and the primary efficacy endpoint.

This is not applicable to Phase 2 since Phase 2 is not powered.

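### Steps 1 and 4 of the Phase 3 hierarchy count only patients on invasive ventilation, so read literally a death scores as favourable and can block the survival claim that follows

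*Combined protocol and SAP*

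**What the plan says.** Section 9.2.1.3 sets the order of testing in Phase 3, each test at 1-sided 0.025. After the primary come "1) proportion of patients on invasive mechanical ventilation at Day 28, (2) proportion of patients alive at Day 28". Step 3 is the primary endpoint moved to Day 60. Then come "4) proportion of patients on invasive mechanical ventilation at Day 60, and (5) proportion of patients alive at Day 60". The gate is strict: "Inferential conclusions about these efficacy endpoints will require statistical significance of the previous endpoints and the primary efficacy endpoint".

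Section 7.1.2 defines the two ventilation endpoints in the same bare form: "Proportion of patients on invasive mechanical ventilation at Day 28" and "Proportion of patients on invasive mechanical ventilation at Day 60; and" Neither mentions death or ECMO. Section 9.1 keeps patients who die in the denominator, since ITT is all randomized patients and "The ITT Population will be the primary population for analysis of efficacy data".

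Where death is meant to count, the protocol says so. The primary and step 3 require the patient to be alive. Section 7.1.3 has "Proportion of patients alive and not hospitalized at Day 28 and at Day 60", and its progression endpoint is a fall on the "NIAID 8-point ordinal scale score or death) at Day 28 and at Day 60".

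Section 9.2.1 has the one general rule. Observed data are used whatever intercurrent events occur. Patients who die or stop treatment before the time point, with a lack-of-efficacy qualifier, and whose status cannot be determined, are treatment failures. Further data handling is left to the SAP; the supplied document has no SAP text on this point.

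**The concern.** Read as worded, a death moves a patient to the good side of steps 1 and 4. That reverses the protocol's own ordering: in Appendix C, Table 4, death is score 1 and invasive ventilation or ECMO is score 2, with higher scores better.

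The harm is mainly a lost survival claim. A drug that saves lives keeps alive some patients who are still ventilated, which weakens literal step 1 and can stop the sequence just before survival is tested. The reverse can also occur: literal step 1 can succeed while deaths are no fewer on drug. The primary counts deaths as failures and gates everything, so a false primary claim is not at issue. Type I error holds under either scoring, provided the scoring is fixed in advance.

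ECMO is a smaller gap. Section 9.2.1.1 lists it apart from invasive ventilation, Table 4 groups the two, and steps 1 and 4 are silent.

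**Working it through.** **Inputs from the protocol.** Section 9.2.5: 60% v 75% response, 152 per arm, 1-sided 0.025, about 80% power. Section 9.2.1.3: order and gate. It gives no Day 28 split of non-responders into dead, on invasive ventilation (IMV) and other support, so **the splits below are assumptions**.

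**The plan's own figure.** The pooled-variance formula gives 152 per arm and 80.0% power. Unpooled: SE = √[(0.60×0.40 + 0.75×0.25)/152] = 0.0530, drift = 0.15/0.0530 = 2.83, power = Φ(2.83 − 1.96) = 80.7%. Obeying the futility boundary (z ≤ 0.789 at 70% information) gives 80.2%, so the interim look is ignored below.

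**One concrete trial** (assumed counts, placebo v drug, 152 per arm):

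| Test | Counts | z | 1-sided p |
|---|---|---|---|
| Primary (responders) | 91 v 114 | 2.85 | 0.002 |
| Step 1, literal (on IMV) | 15 v 15 | 0.00 | 0.50 |
| Step 1, dead or on IMV | 53 v 30 | 3.00 | 0.0013 |
| Day 28 deaths | 38 v 15 | 3.55 | 0.0002 |

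Read literally, the sequence stops at step 1 and the survival result cannot be claimed. In the opposite case (on IMV 30 v 9, deaths 23 v 26), literal step 1 has z = 3.68, p = 0.0001 although deaths are numerically higher on drug. With death as failure it is 53 v 35, z = 2.30, p = 0.011.

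**Power.** Four splits, dead/IMV/other in percent, placebo v drug:

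- (a) 30/8/2 v 18/6/1
- (b) 20/15/5 v the same × 25/40
- (c) 15/20/5 v 10/11/4
- (d) 10/25/5 v the same × 25/40

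For each test, power = Φ(Δ/SE − 1.96) with SE = √[(p₁q₁ + p₂q₂)/152]. In (a):

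- Literal step 1: Δ = 0.08 − 0.06 = 0.02, SE = √(0.1300/152) = 0.0292, power = Φ(0.68 − 1.96) = 10%.
- Redefined step 1: Δ = 0.38 − 0.24 = 0.14, SE = √(0.4180/152) = 0.0524, power = Φ(2.67 − 1.96) = 76%.
- Survival: Δ = 0.30 − 0.18 = 0.12, SE = √(0.3576/152) = 0.0485, power = Φ(2.47 − 1.96) = 70%.

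The tests are correlated, so the joint results come from multinomial simulation (at least 400,000 trials per split at 152 per arm and 200,000 at 304; unpooled z test at 1.96; no stratum adjustment). Chain means that the primary, step 1 and Day 28 survival are all significant. Blocked share is the proportion of trials with primary and survival both significant in which step 1 is not. Paired figures are literal v redefined.

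| Split | Survival power alone | Chain, N = 304 | Blocked share, N = 304 | Chain, N = 608 |
|---|---|---|---|---|
| (a) | 70% | 6% v 64% | 91% v 3% | 15% v 93% |
| (b) | 43% | 12% v 40% | 71% v 4% | 38% v 71% |
| (c) | 26% | 14% v 25% | 46% v 1% | 39% v 46% |
| (d) | 23% | 10% v 20% | 52% v 5% | 31% v 39% |

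Repeat runs agree to about one percentage point. Primary and survival are both significant in 66%, 42%, 25% and 21% of trials at N = 304.

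**Day 60** needs a second layer of assumption. I used three sets of Day 28-to-60 transitions to dead/IMV/other/responder, the same in both arms, with death absorbing:

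- From IMV: 40/20/10/30, 25/40/10/25, 20/60/5/15.
- From other support: 10/5/25/60, 5/5/30/60, 5/5/40/50.
- From responder: 2/0.5/0.5/97, then 1/0.5/0.5/98 in the other two sets.

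Across sets and splits, step 4 power is 4–36% literal v 50–73% redefined. With step 1 already redefined and every other test significant, step 4 blocks Day 60 survival in 69–96% v 1–4%. Part of this is a rare endpoint: control-arm IMV at Day 60 is only 2–16%.

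**The case against.** The best answer is the treatment-failure rule. It opens the efficacy section, names Day 28 and Day 60, and its lack-of-efficacy qualifier can be read as attaching only to stopping treatment. On that reading every death is a failure throughout, and the key secondaries use the primary's method. This may well be the intent. But the wording does not secure it: a dead patient's status is known, so the second condition is not met; failure has no stated value for an endpoint worded as being on ventilation; and the preceding sentence uses observed data regardless. The SAP may settle it, but its text on this point was not available.

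The size is largely assumed, and that stands. Only 60% v 75% and 152 per arm come from the protocol. Split (a) has little IMV, so heavy blocking is built in. In (c) and (d) most of the shortfall is low survival power, and the gap falls to 7–8 points at 608. The simulation also leaves out the stratum adjustment, the futility stop and the promising-zone increase, so the figures illustrate and are not the design's operating characteristics.

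It is also fair that Phase 3 may be amended after Phase 2 and its sample size will be recalculated. That is an occasion to correct the wording, not a reason to leave it.

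**Conclusion.** The concern holds. Two gatekeeping endpoints do not say how a death is scored, and their literal wording scores it as favourable, against the protocol's own scale. It should be fixed, but it does not threaten the primary result or the type I error. Under the assumed splits, the literal reading lowers the chance of a Day 28 survival claim by 10 to 58 points at 304 patients (20 − 10 in (d), 64 − 6 in (a)). The loss is largest when the benefit lies mainly in survival. Confidence is medium, because the intent may be the sensible reading and the SAP may state it. The Day 60 figures are the least certain.

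**What to change.** Define steps 1 and 4 as the proportion alive and free of invasive mechanical ventilation at Day 28 and Day 60, with death from any cause a failure. State how ECMO is counted, for example together with invasive ventilation as in score 2 of Table 4. Align the synopsis (efficacy endpoints and statistical analyses) and Sections 7.1.2, 9.2.1, 9.2.1.2 and 9.2.1.3, so that the two qualifiers in Section 9.2.1 do not limit how deaths are counted here. Do this before any unblinded Phase 3 data are seen, including the interim at 213 patients. A sentence assigning deaths to the on-ventilation category would have the same effect.

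The change is wording only; N, alpha, order and data collection stay. It has two costs. If the drug acts on ventilation only (10/25/5 v 10/11/4), step 1 power falls from about 90% to 78%. The redefined step 1 also overlaps with the primary: after a primary win it is won in 93%, 87%, 92% and 87% of trials in (a) to (d), so it adds little, though this falls to 64% for a 10/15/15 control split reduced proportionally.

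Testing survival before the ventilation step is an alternative. It gives primary plus Day 28 survival in 66%, 42%, 25% and 21%, close to the fix, but the ventilation step would still score a death as favourable.

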9.2.1.4 Pharmacokinetic analysis

PK data will be summarized.

9.2.2 Analysis of Safety

Safety data will be summarized by actual treatment received, and in total for selected analyses/summaries, based on the Safety Population, and include the following:

- AEs and SAEs;
- Clinical laboratory assessments (including clinical chemistry, hematology, and urinalysis);
- Vital signs;
- Physical examinations; and
- 12-lead ECGs.

9.2.3 Analysis Timing

Primary analysis (Phase 2)

A primary analysis will be conducted once all patients in Phase 2 complete the EOT Visit on Day 28 or have discontinued early but would have reached Day 28 had they remained in the study. The results will be conducted by an independent statistician and reviewed by the iDMC following the procedures defined in the iDMC Charter. The iDMC will convene to recommend dose selection

and whether to adjust study design for Phase 3 based on this analysis. The study team will remain blinded. Designated personnel from the Sponsor will have access to the analysis results. The Phase 3 sample size and interim analysis boundaries will be recalculated based on the Phase 2 primary analysis results.

Final analysis (Phase 2 and Phase 3)

For each phase (Phase 2 and Phase 3), after all the patients have completed (discontinued) the study and the database is locked, the data will be unblinded and the final analysis will be performed.

Interim analysis

No interim analysis is planned for Phase 2.

For Phase 3, an interim analysis will be performed once approximately 70% of the randomized patients complete the EOT Visit on Day 28 or have discontinued early but would have reached Day 28 had they remained in the study. The iDMC will convene to evaluate for safety, early futility, and potential sample size recalculation.

For the futility interim analyses, the iDMC will be guided by a pre-specified non-binding futility monitoring boundary based on the gamma family spending function (with parameter $\gamma = -4$, calculated using EAST 6.4, see Table 1). Non-binding for the futility indicates that the futility boundary is constructed in such a way that it can be overruled by the iDMC without inflating the type I error and without decreasing power. The iDMC will also consider all available efficacy and safety data prior to formulating its recommendations regarding continuation or termination of the study due to early futility.

Although the study does not intend to stop early for outstanding efficacy in the interim analysis, a small alpha (0.0001) will be spent in order to protect data integrity and to preserve an overall 1-sided significant level of 0.025 for the primary analysis.

Table 1. Futility Boundaries in the Interim and Final Analyses of Overall Success Rate Based on a 1-Sided Test at the 0.025 Level

Planned Analysis	Total Completers [1]	Information Fraction	Futility Boundary		Boundary Crossing Probability (Incremental)		Cumulative Beta Spent
			Z Scale	Nominal P-Value	Under H_0	Under H_1	
Interim	213	0.7	0.789	0.2151	0.785	0.057	0.0572
Final	304	1	1.960	0.025	0.191	0.141	0.198

1. Patients who complete the Day 28 visit or discontinue early, but would have reached Day 28.

Futility testing (Phase 3)

The process is as follows:

- Futility at the interim analysis: If the 1-sided p-value is ≥ 0.2151 (or the observed z-statistic is ≤ 0.789), then the futility boundary is crossed and the null hypothesis will be accepted; and
- At the final analysis: The final hypothesis is tested at the 1-sided significance level of 0.025.

In case the number of patients at the interim analyses are not exactly equal to the planned number of patients (ie, the first 213 patients who completed the EOT Visit on Day 28 or have discontinued early but would have reached Day 28), the futility boundary will be revised based on the actual number of patients at the interim analysis.

Sample size recalculation (Phase 3)

At the interim analysis for early futility, when the first 213 patients complete the EOT Visit on Day 28 or have discontinued early but would have reached Day 28, the iDMC will also assess for potential sample size recalculation for the study using the promising-zone method. Wald conditional probabilities will be calculated using the actual observed proportions from both treatment arms. The maximum sample size allowed is 608 patients. Sample size will be increased only if the observed data at the interim analysis are promising; that is, if the conditional power is $\geq 36\%$ and $< 80\%$, as described in the SAP.

Possible recommendations by the iDMC

After reviewing the results of the interim analysis, the iDMC may select 1 of 4 or more possible recommendations, based on the test statistics obtained at the interim analysis, as follows:

- Stop for early futility: Stop study early due to strong evidence for futility due to test statistic being in the futility region;
- Continue without change: Continue with no changes due to test statistic not being in the futility region or the conditional power being $< 36\%$ or $\geq 80\%$;
- Add required additional sample size, n, without exceeding the maximum sample size and continue the study; or
- Stop for safety concerns.

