An iDMC will convene to oversee safety and efficacy assessments during and after the Phase 2 study. The first iDMC meeting will occur after approximately 10 to 15 patients have been enrolled. The second iDMC meeting will occur after approximately 50% to 60% of patients have been enrolled. No formal statistical testing will be conducted. In addition, when all patients in the Phase 2 study have completed the EOT Visit on Day 28, a primary analysis will be conducted by an independent statistician and reviewed by the iDMC.

3.1.2 Phase 3

Based on the results of the primary analysis of Phase 2, 1 optimal dose will be selected to carry into Phase 3. Once the optimal dose has been selected, the study may proceed to Phase 3. Patients will be randomized in a 1:1 ratio to receive FP-025 or placebo for 28 days. Similar procedures will be followed as for Phase 2; however, study design (eg, eligibility criteria, sample size number, protocol-defined procedures, and timing of procedures) or dosing may be changed based on iDMC recommendations after data from the primary analysis in Phase 2 becomes available. If the iDMC recommends modification of the protocol, and the Sponsor is in agreement, the protocol will be amended and submitted to regulatory authorities and Institutional Review Boards (IRBs) for approval. An interim analysis will be conducted after approximately 70% (213 out of 304) of the randomized patients have completed the EOT Visit on Day 28 or have discontinued early, but would have reached Day 28 had they remained in the study, to assess for safety, early futility, and potential sample size recalculation.

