9.2.1.1 Primary efficacy analysis

The primary efficacy endpoint is the proportion of patients alive and not requiring non-invasive or invasive ventilation (ie, not receiving high-flow nasal cannula, non-invasive positive pressure ventilation, invasive mechanical ventilation, or ECMO) at Day 28. The treatment group difference of the response proportions, along with the corresponding 95% confidence interval and p-value, will be provided using the logistic regression model by Guo et al. (2012)²⁴ and Ge et al. (2011),²⁵ adjusted for stratification factor (use of invasive mechanical ventilation at the time of randomization [yes or no]). Additional prognostic baseline covariates (eg, age, region, body mass index) may be added as covariates/factors into the model to increase precision in the estimation of difference in proportions. Details will be provided in the SAP.

The primary analysis will be repeated on the PP Population.

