9.2.5 Sample Size Determination

For the Phase 2 study, approximately 99 patients will be randomized in a 1:1:1 ratio to 1 of 3 treatment groups: FP-025 100 mg BID, FP-025 300 mg BID, or placebo BID. No formal statistical assessment for sample size determination has been performed. The sample size is considered adequate to provide the necessary data to evaluate the objectives of the study.

For Phase 3, a total of 304 patients (152 patients per treatment group) will provide approximately 80% power to detect a 15% improvement in response rate, based on a control response rate of 60% and assuming a response rate of 75% with the study drug treatment group, using a 1-sided 0.025 level test. The sample size estimate assumes that an interim analysis will be conducted after approximately 70% of patients (approximately 213 patients) have completed the EOT Visit on Day 28 or have discontinued early, but would have reached Day 28 had they remained in the study, to assess early futility and potential sample size recalculation. The sample size was calculated using EAST 6.4. The Phase 3 sample size will be formally recalculated based on results from the Phase 2 part of the study. A maximum of 608 patients may be included. If the iDMC, in consultation with the Sponsor determines that a sample size of more than 608 patients is needed, a protocol amendment will be required.

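### The interim conditional power is worded as an unadjusted two-proportion calculation, while the final test is adjusted for ventilation stratum; aligning them is a free, minor improvement

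*Combined protocol and SAP*

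**What the plan says.** **Interim rule.** Section 9.2.3 provides for a sample-size review "when the first 213 patients complete the EOT Visit on Day 28" or would have reached that day. For the conditional power it states: "Wald conditional probabilities will be calculated using the actual observed proportions from both treatment arms". The sample size is raised only if that conditional power is at least 36% and below 80%, up to a maximum of 608. Futility is signalled when "the observed z-statistic is ≤ 0.789". The section does not say which model or variance produces that z. It refers to the SAP for details of the promising-zone rule.

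**Final test.** Section 9.2.1.1 specifies a logistic-regression risk difference, "adjusted for stratification factor (use of invasive mechanical ventilation at the time of randomization [yes or no". Further baseline covariates may be added, with details again left to the SAP.

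**Design basis.** Section 9.2.5 states that "a total of 304 patients (152 patients per treatment group) will provide approximately 80% power to detect a 15% improvement in response rate". The rates behind this are 60% on placebo and 75% on FP-025, tested one-sided at 0.025.

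**Allocation.** For Phase 3, section 3.1.2 says: "Patients will be randomized in a 1:1 ratio to receive FP-025 or placebo for 28 days". It does not mention strata. Stratification by IMV is described in sections 3.1.1 and 5.3, in text about Phase 2.

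**The concern.** Conditional power is meant to be the probability that the planned final test succeeds, given the interim data. The wording describes a Wald statistic from two arm proportions, but the test to be run is covariate-adjusted. If IMV at entry predicts being alive and off support at Day 28, the adjusted estimate has the smaller standard error. The 36% and 80% cut-offs would then be applied to a statistic that usually understates the conditional power of the planned test. Some trials could be enlarged although the adjusted test already has 80% conditional power, and others left at 304 although the adjusted result is promising. The rule governs whether the trial grows from 304 to as many as 608 patients.

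**Working it through.** **1. Reproduce the plan's figures.** Inputs from section 9.2.5: 60% vs 75%, 1-sided 0.025, 80% power.

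n per arm = [1.96·√(2·0.675·0.325) + 0.842·√(0.60·0.40 + 0.75·0.25)]² / 0.15² = 151.9, so 152 per arm and 304 in total.

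Table 1, with t = 213/304 = 0.7007: 0.198·(1 − e^(4t))/(1 − e^4) = 0.0572, as printed. A bivariate normal with unpooled variance and no covariates also returns the printed crossing probabilities (0.785 and 0.191 under H0; 0.057 and 0.141 under H1). The stated design figures are therefore reproduced by an unadjusted two-proportion calculation.

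**2. Promising zone on the z scale.** Under the current trend, CP = Φ[(z/√t − 1.96)/√(1−t)], with √t = 0.837 and √(1−t) = 0.547. Inverting:
- CP 36%: z = 0.837·(1.96 − 0.547·0.358) = 1.476
- CP 80%: z = 0.837·(1.96 + 0.547·0.842) = 2.026

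**3. Adjusted against raw z.** The documents give no response rates by IMV stratum. Assumptions: IMV share 1/3 (the minimum stated for Phase 2), overall control rate 60%, +15 points in each stratum, strata balanced between arms.

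The raw variance term is 0.60·0.40 + 0.75·0.25 = 0.4275. The adjusted term is the share-weighted sum of the same expression within strata. For a 30-point gap (control 40% and 70%; FP-025 55% and 85%) it is (1/3)(0.24 + 0.2475) + (2/3)(0.21 + 0.1275) = 0.3875. The ratio is 0.906, so z is multiplied by 1/√0.906 = 1.05. A raw z of 1.476 becomes 1.550, and CP = Φ[(1.550/0.837 − 1.96)/0.547] = Φ(−0.20) = 42%.

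| Control gap | Variance ratio | z factor | Raw CP 36% becomes |
|---|---|---|---|
| 0 | 1.00 | 1.000 | 36% |
| 10 points | 0.99 | 1.005 | 37% |
| 20 points | 0.96 | 1.02 | 39% |
| 30 points | 0.91 | 1.05 | 42% |
| 40 points | 0.83 | 1.10 | 48% |
| 50 points | 0.74 | 1.16 | about 56% |

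An IMV share of one half gives similar values (30-point gap: factor 1.06, CP 43%).

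**4. Change of promising-zone status.** Simulation at +15 points, 400,000 trials per scenario. A stratum-weighted risk difference stands in for the adjusted logistic risk difference.

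| Control gap | Stratified | Unstratified |
|---|---|---|
| 10 points | 1.5% | 5.7% |
| 30 points | 7.5% | 15.8% |
| 50 points | 19% | 21.5% |

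The stratified column is approximate: a separate simulation gave about 1%, 5% and 12% at gaps of 10, 30 and 45 points.

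**5. Operating characteristics.** The final test is adjusted throughout; only the interim decision statistic differs.

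- *Type I error*, futility not enforced: 0.0238 to 0.0254 with the raw decision, 0.0247 to 0.0257 with the adjusted decision.
- *Power at +15 points*, stratified, futility not enforced, raw vs adjusted decision: 0.840 vs 0.841 (10-point gap), 0.867 vs 0.870 (30), 0.922 vs 0.927 (50).
- *Mean sample size*: differs by 0.5 to 7 patients; at a 50-point gap, 325.2 vs 317.9.
- *Power at +10 points*, stratified, futility not enforced: 0.527 vs 0.529 (30-point gap), 0.597 vs 0.607 (50).
- *Worst case seen* (50-point gap, unstratified, futility enforced on the same statistic as the decision): 0.897 vs 0.922 at +15 points (2.6 points lost before rounding), 0.565 vs 0.600 at +10 (3.5 points).

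**6. The 36% cut-off.** For t = 0.70 and a cap of 608, the smallest conditional power at which the conventional final test stays valid is 33.6%, so 36% leaves some room.

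**The case against.** **The wording does not say unadjusted.** Observed proportions may be named only to distinguish the observed effect from the design rates of 60% and 75%. Sections 9.2.1.1 and 9.2.3 defer to the SAP, and no separate SAP section is in the text available, so the SAP may settle the matter. This stands as a caution. Even so, two arm proportions and a Wald statistic describe the unadjusted calculation on their plain meaning, and the design figures fit that reading. For the futility z, no method is stated at all.

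**A reader might infer that IMV is known to be strongly prognostic and that the cut-offs are therefore materially wrong.** The documents do not support that. IMV is the only stratification factor and the NIAID scale ranks it as a worse state than non-invasive support, so some association is the plan's own premise. But no stratum rates are given, and the discrepancy vanishes as the gap goes to zero.

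**A reader might also infer that reclassified interims mean substantial wasted patients or lost power.** Step 5 shows otherwise: most reclassified interims lie near a cut-off, where either decision costs little. Understating conditional power is usually conservative, and type I error is not inflated.

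**Phase 3 may well be stratified.** Section 3.1.2 says that procedures will be similar to Phase 2, and the final model adjusts for the stratification factor. That is plausible but not stated, and the larger losses depend on it.

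**The figures are provisional.** Section 9.2.3 provides for recalculating the Phase 3 sample size and interim boundaries after Phase 2. This is true, and Phase 2 can supply the missing stratum rates.

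**Conclusion.** The point holds as a minor mismatch between the stated interim rule and the stated final test. It is neither a validity failure nor an error in a printed figure. The direction is firm if IMV is prognostic and the strata are balanced: the raw statistic then understates the conditional power of the planned test. With unstratified allocation, chance imbalance can move an individual trial either way.

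The size rests on assumed stratum rates. Over gaps of 10 to 50 points it runs from negligible to a shift of about 20 percentage points in conditional power at the lower cut-off. The practical cost is small at the design effect under stratified allocation. At +10 points with a 50-point gap it is about 1 point of power. It reaches about 2 to 3.5 points only when strongly prognostic IMV, unstratified Phase 3 allocation and enforcement of a futility boundary that the plan calls non-binding are combined.

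**What to change.** In section 9.2.3, the SAP and the iDMC charter:

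- Compute the interim z for futility, the conditional power and any sample-size increase from the same prespecified covariate-adjusted risk difference and standard error as the final primary analysis. The covariates are IMV plus any others, all fixed before the interim. Naming IMV alone would leave a mismatch if age, region or body mass index later entered the final model.
- Give the formula: CP = Φ[(z_adj/√t − 1.96)/√(1−t)] under the current trend.
- State that Phase 3 randomization is also stratified by IMV.

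The cost is a few sentences in three documents. No additional data or patients are needed. When the Phase 3 design is recalculated after Phase 2, the observed stratum rates can replace the assumed gaps above.
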